Electrodes will be placed on the cubital fossa, the most sensitive hollow area on the inside of the elbow [1]. Starting from this reference electrode position (see Figure 2), slight adjustments will be made based on participant feedback to identify the optimal electrode placement that produces a clear electrical tactile sensation at the target site (elbow).

[figure not shown]
<Figure 2. Schematic illustration of electrode placement on the upper limb (elbow)>

1-2) Setting of Stimulation Frequency and Voltage Intensity

The range of stimulation frequencies and voltage intensities that evoke pulsing (flutter) and buzzing (electrical buzzing) sensations was determined. As reported in previous studies, the range for pulsing sensations in terms of stimulation frequency and voltage intensity has been established (see Figure 3). Specifically, the voltage intensity range was set between the minimum voltage at which each participant began to perceive the stimulation (V_{min}) and the maximum voltage at which discomfort was first reported (V_{max}). The frequency range was set from 10 Hz to 70 Hz, the typical upper limit at which participants can distinguish the stimulation.

Based on these criteria, the stimulation frequency and intensity ranges for each sensation were determined. In prior studies conducted by our research group, the maximum tolerable voltage (V_{max}) at which discomfort was reported ranged from approximately 10 to 22 V for both male and female participants [3, 4, 5, 6] (see Figure 3). Generally, females exhibit slightly lower V_{max} values than males (by approximately 0 to 5 V), which is attributed to thinner skin and muscle tissue in females [7].

It is noteworthy that the maximum voltage levels observed for both males and females correspond to approximately 30–70% of the safety voltage standards set by the Occupational Safety and Health Administration. During experiments, electrical stimulation is administered at voltage levels below the participant's discomfort threshold (V_{max}) to ensure safety and comfort.

<Figure 3. Example ranges of electrical stimulation intensity (left) and frequency (right) for individual participants.>

1-3) Measurement of Elbow Angle and Determination of Angle-to-Tactile Conversion Formula

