The elbow angle is measured using a variable resistor (RV09H-20SQ, 50 k Ω). A goniometer marked in 1-degree increments from 0° to 150° is placed on the inner and outer surfaces of a box, aligned with the flexion and extension directions of the elbow joint. Velcro straps are used to secure the participant's upper limb to the inner goniometer, fixing the elbow joint and the distal radius and ulna in place. As the participant moves their arm, the inner goniometer moves accordingly, allowing the current elbow angle to be measured. A pointer is attached to the outer goniometer to enable the participant to indicate the angle. To ensure that the participant cannot

[figure not shown]
see their moving limb, the inner and outer goniometers are enclosed within a box of suitable size, as illustrated in <Figure 4>.

The resistance value measured via the variable resistor is converted into the corresponding elbow angle. Based on the measured elbow angle, the electrical stimulation frequency is adjusted accordingly for the experiment. The conversion formula for mapping elbow angle to electrical stimulation frequency is as follows:

$$F_{stim} = \frac{(F_{max} - F_{min})}{(\theta_{max} - \theta_{target})} (\theta_{current} - \theta_{target}) + F_{min} \quad \theta_{target} \leq \theta_{current} \leq \theta_{max}$$

$$F_{stim} = \frac{(F_{min} - F_{max})}{(\theta_{target} - \theta_{min})} (\theta_{current} - \theta_{target}) + F_{min} \quad \theta_{min} \leq \theta_{current} \leq \theta_{target}$$

θ_{target} denotes the target angle to be learned, which is set differently depending on the experimental condition. θ_{max} and θ_{min} are defined as $\theta_{target} + 15^\circ$, $\theta_{target} - 15^\circ$, respectively. F_{max} and F_{min} are set to 70 Hz and 10 Hz, respectively. $\theta_{current}$ represents the current elbow angle, and F_{stim} denotes the electrical stimulation frequency corresponding to the current elbow angle.

<Figure 4. Box-Type Elbow Angle Measurement Device>

2) Methods

2-1) Study Period

The total study duration spans a minimum of three weeks. For each of the three experimental conditions, assessments are conducted during Visit 1 and Visit 2, with a washout period of at least 7 days between conditions.

2-2) Randomization and Procedure

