All participants enrolled in the study are assigned a random number generated using Python. Based on a pre-defined randomization protocol, each participant is randomly allocated to a specific sequence of the three experimental conditions: Electrical Stimulation Cue, Visual Cue, and No Cue.

2-3) Visit Schedule

All participants receive standard therapy in accordance with clinical guidelines for stroke rehabilitation. The study intervention is provided in addition to standard therapy. A total of six visits are planned. During the screening visit, participants (or their legal representatives) provide written informed consent. The participant's medical history and current clinical status are reviewed to confirm eligibility. Eligible participants are then assigned a randomization number and allocated to a randomized order of the three cueing conditions: Electrical Stimulation Cue, Visual Cue, and No Cue.

Baseline assessments are conducted at Visit 1, Visit 3, and Visit 5—prior to the start of each intervention. After the baseline assessment, one session of the corresponding intervention is administered. Following each intervention session, additional efficacy assessments are performed during all visits. A washout period of at least 7 days is maintained between each experimental condition.

The overall study flow is summarized in Figure 5.

<Figure 5. Study Protocol Flowchart>

2-4) Experimental Intervention Protocols

2-4-1) Electrical Stimulation Cue Protocol

The intervention is administered once for 30 minutes. An electrical stimulation device developed by the research team is attached to the participant's cubital fossa. Stimulation is provided with increasing frequency, reaching a maximum of 70 Hz as the elbow joint approaches a pre-defined target angle. This target angle is individually set within the participant's available range of motion based on baseline assessments. During the session, the participant attempts to match their elbow angle to the target angle while receiving verbal feedback from the examiner.

2-4-2) Visual Cue Protocol

The intervention is administered once for 30 minutes. A visual cue displays the difference between the current elbow joint angle and a predefined target angle on a screen. The target angle is individually set within each participant's range of motion based on baseline assessments. The participant is instructed to match their elbow angle to the target angle while receiving verbal feedback from the examiner.

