Immediately before the experiment, participants will complete a brief questionnaire assessing their sleep duration from the previous night and current physical condition to evaluate readiness for the session. Potential risks will be verbally explained. Participants will be informed that they may withdraw from the study at any point during the procedure for any reason. If severe discomfort arises from the electrical stimulation, the experiment will be terminated immediately.

4-4) Post-experiment Monitoring

Participants will be monitored through questionnaires administered 3 and 7 days after the experiment to assess any adverse effects such as skin allergic reactions or arm discomfort. Safety will be further verified by comparing these responses to those collected prior to the

experiment (Section 4-2).

4-5) Justification for Target Sample Size

This study is a preliminary investigation involving stroke patients, designed to evaluate the feasibility of the study protocol and to estimate effect sizes of key outcome variables. Accordingly, an initial sample size of 10 participants will be recruited. Given the exploratory nature of this pilot study, a limited sample is appropriate for assessing the suitability of the study design, reliability of measurement instruments, and feasibility of procedures. The chosen sample size is consistent with the scale of similar preliminary studies and takes into consideration both the exploratory aims and practical feasibility of the research. The data obtained will provide foundational information necessary for designing future studies and calculating appropriate sample sizes.

5) Study Procedures

5-1) Recruitment and Screening of Clinical Research Participants

Stroke patients admitted to or receiving outpatient treatment at the Department of Rehabilitation Medicine, Severance Hospital, located in Seodaemun-gu, Seoul, will be recruited. After providing an explanation of the study in a private setting, sufficient time will be allowed for participants and their legal guardians to review the information. Written informed consent will be obtained only from those who agree to participate.

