Screening will be conducted exclusively for participants who have provided written consent. The screening process will include a review of medical records, interviews, manual physical examination, and the administration of the Korean Mini-Mental State Examination (K-MMSE) by the investigator to determine eligibility. Participants deemed eligible will be formally enrolled in the study; those who do not meet inclusion criteria will not be enrolled.

5-2) Experimental Site

The evaluation and intervention for this study will take place in the Brain Stimulation Treatment Room on the 6th floor of Severance Rehabilitation Hospital, where the electrical stimulation platform is installed.

5-3) Roles of Collaborative Research Institutions

The Integrated Neuroprosthetics Laboratory at Sungkyunkwan University is responsible for the development, maintenance, and servicing of the electrical stimulation platform used for the intervention.

The Severance Institute for Rehabilitation Medicine is responsible for participant recruitment, clinical intervention, and assessment. The institute consists of one Rehabilitation Medicine professor (principal investigator), one specialist (researcher), and one therapist (researcher). The principal investigator oversees appropriate participant selection and conducts weekly inspections of equipment such as electrical stimulators and electrode patches to prevent accidents. The investigator also has the authority to immediately terminate the experiment if any safety concerns arise during the procedure.

6) Interview Items, Analysis Methods, and Interview Tools

[Post-experiment Questionnaire Items]

1. Did you experience any discomfort in your arm or wrist due to the band, electrodes, or other setup during the experiment?

Not at all		Moderately		Extremely
1	2	3	4	5 or more

2. Did the electrical stimulation help you in perceiving or controlling the angle of your elbow during the experiment?

Not at all		Moderately		Extremely
1	2	3	4	5 or more

3. Did you find the electrical stimulation uncomfortable during the experiment?

Not at all		Moderately		Extremely
1	2	3	4	5 or more

4. Did you perceive the electrical stimulation clearly during the experiment?

Not at all		Moderately		Extremely
1	2	3	4	5 or more

5. Did you pay attention to the information delivered via the electrical stimulation during the experiment?

Not at all		Moderately		Extremely
1	2	3	4	5 or more

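### The stimulation cue is defined in two opposite ways: 10 Hz at the target angle by the section 1-3 formula, 70 Hz by the section 2-4-1 text

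*Protocol*

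**What the plan says.** Two sections of the Protocol define how elbow angle drives stimulation frequency.

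- **Section 1-3** introduces a two-branch formula: "The conversion formula for mapping elbow angle to electrical stimulation frequency is as follows". It states that "F_{max} and F_{min} are set to 70 Hz and 10 Hz, respectively", and it places the upper and lower angle limits 15 degrees above and below the target. It also says that frequency is set from the measured elbow angle during the experiment, so the formula is not confined to method development.
- **Section 2-4-1**, the intervention protocol for this condition, says: "Stimulation is provided with increasing frequency, reaching a maximum of 70 Hz as the elbow joint approaches a pre-defined target angle". It gives no formula of its own, no starting frequency and no angular window.

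Section 1-2 adds only the range: "The frequency range was set from 10 Hz to 70 Hz, the typical upper limit at which participants can distinguish the stimulation". Section 7-3-2 adds only a device cap of 100 Hz. Neither gives a direction, and no text or figure caption says which description prevails.

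**The concern.** The mapping from angle to frequency is the experimental intervention. In section 1-3 a high frequency means that the elbow is far from the target. In section 2-4-1 a high frequency means that it is close. Staff cannot follow both, although section 12 requires strict adherence to the protocol.

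Three things are at stake:

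- **Reproducibility and reporting.** Section 4-5 describes a pilot "designed to evaluate the feasibility of the study protocol and to estimate effect sizes of key outcome variables". If the wrong section is taken as the description of what was delivered, those effect sizes are attached to a cue that participants did not receive, and a later trial would be built on it.
- **Coordination between sites.** Under section 5-3 one institution "is responsible for the development, maintenance, and servicing of the electrical stimulation platform used for the intervention", while the other "is responsible for participant recruitment, clinical intervention, and assessment". Both need the same written rule.
- **Bias, conditionally.** If the device were programmed from one section and participants instructed from the other, the cue could mislead them and distort the comparisons of the Electrical Stimulation Cue with the Visual Cue and No Cue conditions.

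**Working it through.** **Inputs, all from section 1-3:** F_max = 70 Hz; F_min = 10 Hz; θ_max = θ_target + 15°; θ_min = θ_target − 15°. Write d = θ_current − θ_target, and e for the absolute value of d.

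**Upper branch (d from 0 to +15):**
F = (F_max − F_min)/(θ_max − θ_target) × d + F_min = (60/15) × d + 10 = 10 + 4d

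**Lower branch (d from −15 to 0):**
F = (F_min − F_max)/(θ_target − θ_min) × d + F_min = (−60/15) × d + 10 = 10 − 4d

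Since d is zero or negative in the lower branch, both branches equal **F = 10 + 4e**. The result does not depend on the target angle or on the side of approach. Evaluating the formula at targets of 30°, 60°, 90° and 120° gave the same values each time.

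**Comparison with section 2-4-1.** That section fixes only the direction (rising) and the maximum of 70 Hz on approach to the target. To show the gap away from the target, I *assume* the mirror-image linear map over the same window, F = 70 − 4e. The absolute difference between the two maps is then the absolute value of 60 − 8e.

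| Distance from target, e | Section 1-3 formula | Section 2-4-1, assumed mirror image | Difference |
|---|---|---|---|
| 0° | 10 Hz | 70 Hz | 60 Hz |
| 5° | 30 Hz | 50 Hz | 20 Hz |
| 7.5° | 40 Hz | 40 Hz | 0 Hz |
| 10° | 50 Hz | 30 Hz | 20 Hz |
| 15° | 70 Hz | 10 Hz | 60 Hz |

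The formula column, the 70 Hz maximum and the opposite direction come from the Protocol. The other values in the third column, and the differences away from the target, rest on the mirror-image assumption.

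**Could this be a text-extraction error?** It is unlikely. The numerator is reversed in the lower branch, which is what makes the two branches meet at 10 Hz and form a consistent V with its minimum at the target. A reading error would have had to alter both branches coherently.

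**The case against.** The contradiction itself is hard to dispute. The case on the other side concerns its consequences.

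- **The two maps carry the same information.** Over the window, 10 + 4e and 70 − 4e are each one-to-one in e with the same slope of 4 Hz per degree. If one is delivered and explained consistently, the participant receives an equivalent error signal. Nothing in the Protocol says that direction affects efficacy. This stands. The harm then is misdescription, which could be corrected from the device program.
- **The bias route is hypothetical.** Frequency is computed from the sensor angle, not chosen by an operator. The Protocol does not tell participants to seek the highest or the lowest frequency, and the examiner gives verbal feedback throughout the session, which might expose a mismatch. This also stands. Dividing development and delivery between institutions is ordinary and is not evidence of a mismatch.
- **The outcome link is indirect.** Efficacy assessments follow the session, and none is described as performed with the cue switched on. A frequency gap during training therefore does not translate directly into an error of similar size in an endpoint. This stands.
- **Safety is unaffected.** Both maps stay within 10 to 70 Hz, below the 100 Hz cap. This stands.

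None of these points says which section is correct. The defining property of the experimental cue is still stated in two incompatible ways.

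**Conclusion.** The concern holds, and the text must be corrected. At the target angle the Protocol specifies both 10 Hz and 70 Hz, a gap of 60 Hz that spans the whole stimulation range, with opposite directions of change on approach. This rests only on the stated constants and formula. The size of the gap at intermediate angles rests on the assumed mirror-image map.

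The established harm is to the description and reproducibility of the intervention. Biased contrasts would follow only from a mismatch between device and instruction, which the Protocol neither shows nor rules out. In the particular case where the device ran the formula and a participant sought the highest frequency, the 70 Hz point would lie 15° from the target. The documents do not show which direction was intended, and I do not assume one. The figures are not available to me and might illustrate the mapping, but no caption says that they do.

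**What to change.** Adopt one mapping and state it identically in sections 1-3 and 2-4-1.

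- **Option A, keep section 2-4-1:** swap F_max and F_min in both branches of the formula, giving F = 70 − 4e within 15° of the target.
- **Option B, keep the formula:** reword section 2-4-1 to say that frequency decreases from 70 Hz at 15° off target to 10 Hz at the target.

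Under either option:

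1. Align the examiner's instruction to participants with the chosen direction.
2. Before the first participant, check the programmed device at 0°, ±5°, ±10° and ±15°. Expected output is 70, 50, 30 and 10 Hz under A, or 10, 30, 50 and 70 Hz under B.
3. As a minor clarification, add one line on the output beyond 15°, which is not stated; holding the boundary value is one choice.
4. Section 9 schedules experiments to begin after July 1, 2025. If anyone has already been treated, record which mapping they received.

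The cost is an edit to one formula or one sentence, one added line, and one bench check. No patients, visits or design changes are involved.

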2-4-3) No Cue Protocol

The intervention is administered once for 30 minutes. The participant attempts to match their elbow joint angle to a verbally instructed target angle, relying solely on verbal feedback from the examiner.

2-5) Outcome Measures and Assessment Procedures

2-5-1) Threshold Detection

An angle-detecting sensor developed by the research team (see Section 1-3) is attached to the participant's affected elbow joint. The examiner holds the medial and lateral epicondyles of the participant's affected upper limb with one hand and the distal radius and ulna with the other. The test is conducted four times in total: two trials in the flexion direction and two in the extension direction, in random order. Each trial starts from 60° of elbow flexion. The examiner moves the joint at approximately 6° per second, and the participant is instructed to verbally report when they perceive joint movement. If the participant does not respond before the joint reaches 30° of motion, a score of 0 is recorded.

-2 points: Participant perceives movement of the elbow joint.

-0 points: Participant does not perceive movement of the elbow joint.

2-5-2) Joint Position Reproduction

[figure not shown]
An angle-detecting sensor developed by the research team is attached to both of the participant's elbow joints. The examiner holds the medial and lateral epicondyles of the participant's affected upper limb with one hand and the distal radius and ulna with the other. The examiner passively moves the affected arm to one of 12 pre-defined flexion or extension angles in the following order: 60°, 90°, 30°, 120°, 60°, 30°, 90°, 120°, 30°, 60°, 120°, and 90°. After each presentation, the participant is asked to reproduce the same angle using the unaffected limb. The average difference between the target angles and the reproduced angles across the 12 trials is calculated and used for analysis.

2-5-3) position Sense Test

Apparatus

Goniometers marked in 1-degree increments from 0° to 120° are installed on the inner and outer surfaces of a box aligned with the elbow joint's flexion and extension axis. Velcro straps are used to secure the participant's upper limb and distal radius and ulna in place. A pointer is attached to the outer goniometer to allow the participant to indicate the perceived angle. A box of appropriate size is placed between the inner and outer surfaces to block the participant's view of their own arm during the test.

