* The apparatus was newly designed with reference to the Wrist Position Sense Test Apparatus (see Figures 4 and 6).

<그림 6. Wrist position sense test apparatus>

Procedure

The examiner passively moves the participant's upper limb to one of 12 predefined elbow flexion or extension angles in the following order: 60°, 90°, 30°, 120°, 60°, 30°, 90°, 120°, 30°, 60°, 120°, and 90°. The examiner attempts to maintain a consistent speed during both flexion and extension movements. After the target angle is reached, the participant uses their contralateral (unaffected) hand to indicate the perceived angle by adjusting a pointer on the outer goniometer of the device. The absolute differences between the presented and indicated angles are recorded for each of the 12 trials, and the average error is calculated for analysis.

2-5-4) Motor & Position Sense Test

Apparatus

Goniometers marked in 1-degree increments from 0° to 120° are installed on both the inner and outer surfaces of a box aligned with the flexion and extension axis of the elbow joint. Velcro straps are used to secure the participant's upper limb, including the elbow joint and distal radius and ulna. A pointer is attached to the outer goniometer to allow participants to indicate perceived joint angles. A box of appropriate size is placed between the inner and outer goniometers to ensure that the participant's tested arm remains out of view during the assessment.

Procedure

After assessing the participant's upper limb range of motion (ROM), the examiner manually moves the goniometer pointer to present 12 different target angles within the participant's available ROM. The participant is instructed to actively move their elbow joint to match the presented angle by flexing or extending the joint. During each trial, the participant is encouraged to move at a consistent speed. After the examiner presents the target angle using the pointer, the participant moves their limb to the angle they perceive as matching the target. The difference between the presented and perceived angles is recorded for each of the 12 trials, and the average error is calculated for analysis.

2-5-5) Fugl-Meyer Assessment (FMA): Upper Limb Position Sense Test

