3) Participant Selection and Exclusion Criteria

3-1) Inclusion Criteria: Participants meeting all of the following criteria will be included

- ① Patients diagnosed with ischemic or hemorrhagic stroke.
- ② Stroke confirmed by CT or MRI imaging.
- ③ Presence of proprioceptive sensory impairment associated with stroke.
- ④ Chronic phase stroke patients, at least 3 months post-stroke onset.
- ⑤ Ability to voluntarily flex and extend the elbow joint.
- ⑥ Age 19 years or older.
- ⑦ Written informed consent provided voluntarily by the participant or their legal representative.

3-2) Exclusion Criteria: Participants meeting any of the following criteria will be excluded

- ① K-MMSE score < 10 or severe aphasia making communication difficult.
- ② Severe pain during elbow joint movement.
- ③ Presence of elbow joint contracture, spasticity, ataxia, musculoskeletal disorders, fractures unhealed ulcers, or open wounds.
- ④ Progressive or unstable stroke condition.
- ⑤ Presence of unilateral neglect.
- ⑥ Coexisting significant neurogenic disorders.
- ⑦ Presence of major psychiatric disorders such as major depressive disorder, schizophrenia, bipolar disorder, or dementia.
- ⑧ Presence of a pacemaker.

4) Recruitment and Management of Study Participants

Ten chronic stroke patients with proprioceptive sensory impairment will be recruited. Recruitment will be conducted among inpatients at Yonsei Severance Hospital. Participants and their legal representatives will be provided with an explanation by a physician or research staff regarding the study details outlined below under 'Experimental Procedures' and will make an informed decision regarding participation.

4-1) Explanation of the Experimental Procedure

This experiment is conducted with the purpose of enabling participants to perceive the position of the arm by delivering information about the elbow joint angle through electrical stimulation.

Electrical stimulation refers to the application of current through electrodes attached to the skin, using a voltage supply device with current limitations. The applied voltage and current levels comply with safety standards set by the Korea Occupational Safety and Health Agency and the Ministry of Food and Drug Safety, specifically “voltages not exceeding 30 V and currents not exceeding 50 mA,” which are considered safe for human exposure.

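### Threshold Detection is scored 2 or 0 at one 30° cut-off, so the stated score gives no threshold and cannot show improvement below 30°

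*Protocol*

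**What the plan says.** The assessment is headed "2-5-1) Threshold Detection" (Protocol, Outcome Measures and Assessment Procedures). It runs four trials, two in flexion and two in extension, each from 60° of flexion.

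- Equipment: "An angle-detecting sensor developed by the research team (see Section 1-3) is attached" to the affected elbow.
- Procedure: "The examiner moves the joint at approximately 6° per second, and the participant is instructed to verbally report when they perceive joint movement".
- Scoring: "2 points: Participant perceives movement of the elbow joint", and 0 points if it is not perceived. "If the participant does not respond before the joint reaches 30° of motion, a score of 0 is recorded".

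The section does not say that the angle or time at the report is recorded, averaged or analysed. It has no intermediate score and no rule for combining the four trials.

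The next three tests are handled differently. Sections 2-5-2 to 2-5-4 each take an angular difference in degrees and average it over 12 trials. In 2-5-3, for example: "The absolute differences between the presented and indicated angles are recorded for each of the 12 trials".

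Section 4-5 gives the purpose of the pilot as feasibility, instrument reliability and "to estimate effect sizes of key outcome variables".

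**The concern.** A detection threshold is the smallest movement a person can feel, in degrees. The stated score answers a narrower question: did the participant report anything before 30°? Any earlier report earns the same 2 points.

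A participant who already detects before 30° on all four trials is at the maximum at baseline and cannot improve. If most of the sample is in that position, the pilot cannot tell an ineffective cue from a test at its ceiling. The estimated effect would be close to zero, or undefined on a standardised scale if nobody's score varies. That would misinform the sizing of the next study, which section 4-5 says these data are meant to support.

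**Working it through.** The protocol gives no figure to reproduce here. The check applies the scoring rule as written and then illustrates its consequences.

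**Inputs from section 2-5-1:** four trials, about 6° per second, cut-off 30°, score 2 or 0.

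**Assumed:** the points are awarded per trial (the cut-off sentence suggests this but does not say it), the four scores are summed, and all distributions of detection angle.

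**1. Response window.** 30° ÷ 6° per second = 5 s. A report at 2° (2 ÷ 6 ≈ 0.3 s) and one at 29° (29 ÷ 6 ≈ 4.8 s) both score 2. The sum can only be 0, 2, 4, 6 or 8.

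**2. Ceiling.** If a trial is detected with probability p, independently, the chance of the maximum is p⁴: 6% at p = 0.5, 24% at 0.7, 66% at 0.9 and 81% at 0.95.

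**3. Response to improvement in one participant.** Let the report angle be normal with mean m and SD s. The expected sum is 8 × Φ((30 − m)/s). The threshold falls from 20° to 5°, a 75% reduction.

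| Assumed s | Sum at 20° | Sum at 5° | Change |
|---|---|---|---|
| 3° | 7.997 | 8.000 | 0.003 |
| 5° | 7.818 | 8.000 | 0.18 |
| 8° | 7.155 | 7.993 | 0.84 |

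**4. Group comparison (simulation, 20,000 runs).** Ten participants are measured before and after, with a 30% fall in threshold. A paired t-test is applied to the summed score and to the mean log angle capped at 30°.

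- Model A: log-normal detection angle, log-SD 0.5 between and 0.4 within persons.
- Model B: A plus visit-to-visit and effect variation, log-SD 0.3 each.
- Model C: B plus a verbal delay with mean 0.5 s (0.5 × 6 = 3°), SD 0.15 s between and within persons.
- Model D: B plus a delay with mean 1.0 s (6°), SD 0.3 s between and within persons.

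Chance of p<0.05, score / angle, in %:

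| Median threshold | At ceiling at baseline (A) | A | B | C | D |
|---|---|---|---|---|---|
| 6° | 98 | 0 / 94 | 0 / 40 | 0 / 36 | 0.1 / 31 |
| 10° | 88 | 0.5 / 94 | 0.7 / 40 | 1.3 / 39 | 3.0 / 36 |
| 15° | 69 | 10 / 93 | 6 / 40 | 9 / 39 | 13 / 37 |
| 20° | 50 | 31 / 91 | 14 / 39 | 17 / 38 | 21 / 36 |
| 25° | 35 | 47 / 87 | 21 / 37 | 23 / 36 | 25 / 33 |
| 30° | 24 | 55 / 81 | 25 / 34 | 26 / 33 | 27 / 29 |
| 40° | 11 | 57 / 64 | 27 / 27 | 27 / 25 | 26 / 21 |

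With the longer delay of model D, the share at ceiling is lower: about 93, 76, 53 and 36% at medians of 6, 10, 15 and 20°.

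The angle is clearly better up to about 20° to 25°. Its advantage shrinks at 30°. At 40° it survives only in model A, is nil in B, and is reversed in C and D.

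**The case against.** **The section is silent on the angle; it does not discard it.** A sensor is attached and the participant reports when movement is felt, so the angle may well be captured. The choice of analysed variable and the way trials are combined can be left to an analysis plan that is not shown. This limits the claim to the stated score. But the protocol does fix the result as 2 or 0, the sensor may serve only to set the start and the cut-off, and no later plan can recover an angle that was not captured at the visit.

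**The illustration has no anchor in the document.** This stands. The trial enrols people with "Presence of proprioceptive sensory impairment associated with stroke", and no detection rates are given. If typical thresholds are near or above 30°, the fixed cut-off is not inferior. The significance yardstick is also imperfect, because this is a three-condition pilot aimed at estimation, and the simulation uses one before-after pair.

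**Bias is too strong a word.** A detected/not-detected result has an effect of its own. It is biased toward zero only if the target is the detection angle, although the test's name suggests that it is.

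**The angle is noisy.** Movement is by hand and the report is verbal, in patients whose K-MMSE may be as low as 10. This also stands, and models C and D show its cost. It does not turn a two-level score into a threshold.

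**Conclusion.** The concern holds for the score as stated. It follows from the scoring rule alone that section 2-5-1 yields no threshold in degrees and that improvement remaining below 30° does not register. Improvement from beyond 30° to below it still does.

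The practical loss cannot be computed from the protocol. On the assumed inputs it is severe for median thresholds up to about 15°, moderate at 20° to 25°, and small or absent from 30° to 40° once visit and effect variation are allowed for.

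Importance is low to moderate. This is one of eight assessments, none is named primary, and three others already measure elbow position sense in degrees. Those three do not replace a movement-detection threshold, so the change is worth making.

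**What to change.** In section 2-5-1:

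- State that the sensor displacement from the 60° start, in degrees, is recorded at the verbal report in each of the four trials.
- Define the analysed quantity as the mean or log-mean over the four trials, with non-response treated as censored at 30°.
- Keep the 0/2 score as a descriptive summary, and say whether it is given per trial and how the four are combined.
- Note that the angle includes verbal reaction time (about 3° per 0.5 s) and variation in hand-moved speed, so absolute values need care.

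The cost is a few sentences, one extra recorded value per trial and a way to mark the moment of the report. Section 1-3 describes measurement of the current angle but no event marker. No trials or visits are added.
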